### **2.1.3.1 Relapse Related Efficacy Endpoints**

Relapse is defined as new neurological symptoms or worsening of previous neurological symptoms with an objective change on neurological examination. Symptoms must be attributable to MS, last at least 48 hours, be present at normal body temperature (i.e., no infection, excessive exercise, or excessively high ambient temperature), and be preceded by at least 30 days of clinical stability.

MS relapse will be verified at each visit. On the other hand, patients will be informed to contact the Study Investigator as soon as they observe any sign/symptom compatible with a possible relapse, in order to schedule an extra visit.

#### **2.1.3.1.1 Annualized Relapse Rate**

The number of patients with a relapse event, the total number of relapses, and the annualized relapse rate over the years of follow-up will be produced.

#### **2.1.3.1.2 Proportion of Patients who are Relapse Free**

Patients will be considered relapse free at each measurement time and at the end of the study if they did not experience a protocol defined relapse in the relevant time period.

### **2.1.3.2 Expanded Disability Status Scale (EDSS)**

Patient disability will be evaluated using the EDSS, which has long been considered the standard for assessing disability in patients with MS.

EDSS will be collected at D1 (if not collected in the previous 3 months) and then at each scheduled visit (every 6 months) and unscheduled visits for MS relapse. For the change from baseline in EDSS analysis, unscheduled EDSS assessments will not be used (except for early study discontinuation assessments).

### **2.1.3.3 Brain imaging**

Brain imaging will be performed at D1 (if not performed in the previous 6 months) and then every 12 months. It will be also performed at the end of study visit, if not performed in the previous 6 months. MRIs will be read and interpreted locally by qualified site personnel and/or designee (e.g., neuroradiologist). MRIs should be reviewed locally by qualified site personnel for signs of Non-MS pathology. For study purposes, per-protocol scans will be also submitted to a central imaging vendor for scan quality control and analysis.

#### **2.1.3.3.1 Number of lesions**

The cumulative count is the primary interest, which is defined as the sum of the lesion counts at each successive year from the D1 screening to the end of study. The lesion counts will also be analyzed yearly.

#### **2.1.3.3.2 Volume of lesions and BPF**

Percentage change of T1 and T2 volume as well as brain parenchymal function (BPF) are the primary interest, which is defined as absolute difference between post-baseline result and baseline result divided by the baseline times 100%.

### **2.1.4 Safety endpoints**

The safety endpoints are the primary endpoint for this study.

The safety analysis will be based on the reported adverse events and other safety information, such as clinical laboratory data and vital signs.

#### ***Observation period***

The on-study observation period is defined as the time from start of screening visit until the end of the study (defined as last protocol planned visit or the resolution/stabilization of all serious adverse events and adverse events with prespecified monitoring).

#### **2.1.4.1 Adverse events variables**

All adverse events will be coded to a lower-level term (LLT), preferred term (PT), high-level term (HLT), high-level group term (HLGT), and associated primary system organ class (SOC) using the version of Medical Dictionary for Regulatory Activities (MedDRA) currently in effect at Sanofi at the time of database lock OR specify version if already known from project specifics.

Incidence, duration, grade/intensity, relationship to study drug, and outcome of the AE will be analyzed for serious adverse events (SAEs), adverse events (AEs), infusion-associated reactions (IAR).

Incidence, nature, seriousness, grade/intensity, relationship to study drug, and outcome will be summarized for the project-specific adverse events of special interest (AESIs).

Record the occurrence of adverse events (including serious adverse events and adverse events of special interest) from the time of signed informed consent until the end of the study.

**Adverse events of special interest** include the following terms:

- Hypersensitivity or anaphylaxis
- Pregnancy of a woman entered in the study;

- Pregnancy occurring in a woman patient entered in the clinical trial. It will be qualified as an SAE only if it fulfills one of the seriousness criteria.
- Follow-up of the pregnancy in a woman participant is mandatory until the outcome has been determined.
- Symptomatic overdose (serious or non-serious) with IMP.
  - An overdose (accidental or intentional) with the IMP is an event suspected by the Study Investigator or spontaneously notified by the patient and defined as increase of at least 30% of the dose to be administered in the specified duration or if the dose is administered in less than half the recommended duration of administration.  
  
Of note, asymptomatic overdose must be reported as a standard AE.
- Increase in alanine transaminase (ALT).
- Other product specific AESIs:
  - Autoimmune mediated conditions including, but not limited to:
    - Immune thrombocytopenic purpura (ITP).
    - Nephropathies including anti-glomerular basement membrane (GBM) disease.
    - Cytopenias.
    - Thyroid disorders.
    - Acquired hemophilia A
    - Autoimmune hepatitis.
  - Hemophagocytic lymphohistiocytosis (HLH).
  - Progressive multifocal leukoencephalopathy (PML)
  - Temporally associated\* pulmonary alveolar hemorrhage
  - Temporally associated\* myocardial ischemia, myocardial infarction
  - Temporally associated\* stroke
  - Temporally associated\* cervicocephalic arterial dissection  
(\* Temporally associated: 1 to 3 days after the last infusion)
  - Serious infections including serious opportunistic infections (eg, Listeria infections, CMV, EBV), HPV associated with cervical dysplasia
  - Malignancy.
  - Pneumonitis

The standardized MedDRA queries (SMQ) or Custom MedDRA queries (CMQ) will be applied as appropriate to select AESIs.

**Infusion-associated reactions (IAR)** is defined as any adverse event occurring during and within 24 hours of alemtuzumab infusion. It will be analyzed separately for retreated patients.

#### **2.1.4.2 Deaths**

The deaths observation period are per the observation periods defined above.

- Death on-study: deaths occurring during the on-study observation period
- Death poststudy: deaths occurring after the end of the study

#### **2.1.4.3 Laboratory safety variables**

Clinical laboratory data consists of blood analysis, including hematology, clinical chemistry, and urinalysis. Clinical laboratory values after conversion will be analyzed into standard international units and international units will be used in all listings and tables.

For patients exposed to alemtuzumab within 48 months prior to inclusion in this study, samples for clinical laboratories will be taken at monthly for CBC with differential (including platelet count), serum creatinine, liver function and urinalysis. TSH must be obtained every 3 months and HPV test should be performed yearly until 48 months after the last infusion of alemtuzumab administered in the study CAMMS03409.

For patients exposed to alemtuzumab during this study, pregnancy test, HPV test must be obtained before the infusion in TOPAZ study if they were not done within 12 months prior to the treatment. CBC with differential (including platelet count), serum creatinine, TSH, liver function test (ALT, AST, ALP, albumin, total protein, direct bilirubin and total bilirubin) and urinalysis (minimally including determination of urine protein and red blood cells) with microscopy are also required to be assessed before alemtuzumab infusion if they were not assessed within 2 weeks prior to treatment. Samples for CBC with differential (including platelet count), serum creatinine, liver function and urinalysis will be analyzed monthly. The TSH will be performed quarterly. The HPV test will be performed yearly. In addition, unscheduled liver function tests may be performed at any time if clinically indicated at Investigators' discretion.

The laboratory parameters will be classified as follows:

- Hematology
  - **Red blood cells and platelets and coagulation:** hemoglobin, hematocrit, red blood cell count, platelet count
  - **White blood cells:** white blood cell count, neutrophils, lymphocytes, monocytes, basophils, eosinophils
- Clinical chemistry
  - **Renal function:** creatinine, creatinine clearance
  - **Liver function:** alanine aminotransferase, aspartate aminotransferase, alkaline phosphatase, total protein, albumin, direct bilirubin and total bilirubin

- TSH

Urine samples will be collected minimally including determination of urine protein and red blood cells with microscopy.

#### **2.1.4.4 Vital signs variables**

Vital signs include systolic and diastolic blood pressure (millimeters of mercury [mmHg]), heart rate (beats/minute [bpm]), respiratory rate (breaths/minute), body temperature (degrees Celsius [°C]) and weight (kg).

- For all the patients: vital signs will be recorded at selection visit (D1) (if not recorded in the previous 3 months) and then every 6 months.
- For patients treated with alemtuzumab: on days when alemtuzumab is infused, vital signs will be recorded before steroid administration, at a time after steroid administration (prior to alemtuzumab infusion), and 1 hour after the start of alemtuzumab infusion and hourly during and after infusion until observation post-infusion has ended (two hours after the end of the infusion).

#### **2.1.4.5 Electrocardiogram variables**

ECG is required within 2 weeks prior to alemtuzumab infusion including heart rate, PR, QRS, QT, and corrected QTc (according to Bazett/Fridericia).

#### **2.1.5 Quality-of-life endpoints**

Questionnaires including MOS 36-item short-form health survey (SF-36) Version, Functional Assessment of Multiple Sclerosis (FAMS), EuroQoL in 5 dimensions (EQ-5D) will be assessed on selection visit (D1) and every 12 months.

- Change over time in self-reported quality of life (QoL) as assessed by the Medical Outcome Study (MOS) 36-Item Short-Form Health Survey (SF-36) Version 2.
- Change over time in the Functional Assessment of Multiple Sclerosis (FAMS), and
- Change over time in the EuroQoL in 5 Dimensions (EQ-5D).

##### **2.1.5.1 Medical Outcomes Study Short Form-36, Version 2**

The SF-36 is an extensively validated and widely used measure of quality of life (QoL) that assesses patients' perceptions of health status and its impact on their lives (1). It consists of 36 items organized into 8 scales (physical functioning, social functioning, role limitations physical, bodily pain, general medical health, mental health, role limitations emotional, and vitality). Two summary measures of physical and mental health, the Physical Component Summary (PCS) and Mental Component Summary (MCS), respectively, are derived from scale aggregates. Higher scores are associated with better QoL.

SF-36 scores will be transformed using general US population norms so that all scales have a mean of 50 and a standard deviation of 10 as described in the SF-36 Users Manual (2). Therefore, scores can be directly compared across scales, as well as to the general population norm of 50.

#### **2.1.5.2 Functional Assessment of Multiple Sclerosis (FAMS), Version 4**

The FAMS is a widely accepted, MS-specific, quality of life questionnaire (3)(4). The FAMS is a self-report multidimensional index comprising a total of 58 items on 7 subscales: mobility (7 items); symptoms (7 items); emotional well-being (7 items); general contentment (7 items); thinking and fatigue (9 items); family/social well-being (7 items); and additional concerns (14 items, these are not scored). Each item (except those for “additional concerns”) is rated on a 5-point scale of 0 to 4. The sum of the 44 scored items is the total score, which ranges from 0 to 176. A higher FAMS score reflects a higher quality of life. The total score is the primary criterion by which the effect of treatment on quality of life will be assessed; however, subscale totals will also be evaluated.

#### **2.1.5.3 EuroQoL-5D (EQ-5D)**

The EQ-5D is a generic, standardized instrument that provides a simple, descriptive profile and a single index value for health status (4)(5). The EQ-5D comprises 5 dimensions of health: mobility, self-care, usual activities, pain/discomfort, and anxiety/depression. Each dimension consists of 3 levels (some, moderate, extreme problems), generating a total of 243 theoretically possible health states. Country-specific value sets convert these health states into utility scores describing the preference of the population for one health state over another.

Assessments will also be made using the EQ Visual Analogue Scale (EQ-VAS), which captures the self-rating of current health status using a visual "thermometer" with the end points of 100 (best imaginable health state) at the top and zero (worst imaginable health state) at the bottom.

### **2.1.6 Other endpoints**

#### **2.1.6.1 Modified healthcare resource utilization questionnaire (HRUQ) / Health related productivity questionnaire (HRPQ)**

Patients' use of healthcare resources, non-medical resources, and informal care as well as their work capacity will be assessed at scheduled study visits using modified healthcare resource utilization questionnaire (HRUQ) and health related productivity questionnaire (HRPQ) designed to evaluate the economic impact of MS.

- The questionnaire addresses the following content areas:
- Employment situation and changes in employment situation due to MS
- Admissions and stays in hospital, rehabilitation centers, or nursing homes
- Typical MS-related investments (eg, stair and bed lift, ramps, rails) and devices (eg, walking aids, wheelchairs)

- Assistance by community or social services (eg, home nurse, transportation), or help from family or friends.
- Patient reported data regarding employment status.

Information on resource use is obtained retrospectively, and each type of resource is collected for a time period that would minimize recall bias.

Each question requires a binary answer (yes/no) followed by details on the type and quantity of the resource. All resources that are expected to be used are prespecified in order to minimize errors due to spelling, and hence no open fields or free text (eg, “other”) are permitted.

Modified HRUQ / HRPQ will be collected at D1 (if the HRUQ questionnaire was administered in the previous 3 months, then only questions 1 through 10 of the Modified HRUQ/HRPQ need to be completed at baseline, D1). The modified HRUQ / HRPQ will continue to be collected every 12 months and at the end of study visit.

## 2.2 DISPOSITION OF PATIENTS

This section describes patient disposition for both patient study status and the patient analysis populations.

Screened patients are defined as any patients who signed the informed consent.

For patient study status, the total number of patients in each of the following categories will be presented in the clinical study report using a flowchart diagram or summary table:

- Enrolled patients
- Screen failure patients and reasons for screen failure
- Retreated patients
- Patients who did not complete the study period as per protocol
- Patients who discontinued study period by main reason for permanent treatment discontinuation

For all categories of patients, percentages will be calculated using the number of all enrolled patients as the denominator. Reasons for treatment discontinuation will be supplied in tables giving numbers and percentages in overall group, retreated group and by subgroups (IAT vs DAT).

All critical or major deviations will be summarized in tables giving numbers and percentages of deviations in overall group and by subgroups (IAT vs DAT).

Additionally, the analysis populations for safety, efficacy, and subgroup population (see [Section 2.3](#)) will be summarized in a table by number of patients on the enrolled population.

- Safety population

- Retreated population
- 48 months follow-up population
- Efficacy population
- Subgroup population
  - IAT population
  - DAT population

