#### 8.1.1 Administration

There is no fixed treatment requirement or schedule. Administration of alemtuzumab will only be done following a decision from the Study Investigator that an additional “as needed” course is indicated.

Alemtuzumab will be then administered by IV infusions in a supervised medical setting at a dose of 12 mg/day on 3 consecutive days (36 mg total dose) at least 12 months after the prior treatment course.

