## **10.3 HANDLING OF PATIENT TREATMENT DISCONTINUATION AND OF PATIENT STUDY DISCONTINUATION**

Any IMP discontinuation should be fully documented in the e-CRF. In any case, the patient should remain in the study as long as possible.

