### **10.3.1 Permanent treatment discontinuation with investigational medicinal product(s)**

Permanent treatment discontinuation is any treatment discontinuation associated with the definitive decision from the Study Investigator or the patient not to re-expose the patient to the IMP at any time.

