##### ***Analysis of all treatment-emergent adverse events***

The following treatment-emergent adverse event summaries will be generated for the safety population.

- Overview of treatment-emergent adverse events, summarizing number (%) of patients with any
  - Treatment-emergent adverse event
  - Serious treatment-emergent adverse event
  - Treatment-emergent adverse event leading to death
  - Treatment-emergent adverse event leading to permanent treatment discontinuation
- All treatment-emergent adverse event by primary SOC, HLGT, HLT, and PT, showing number (%) of patients with at least 1 treatment-emergent adverse event sorted by the SOC

internationally agreed order. The other levels (HLGT, HLT, PT) will be presented in alphabetical order

- All treatment-emergent adverse events by primary SOC and PT, showing the number (%) of patients with at least 1 treatment-emergent adverse event, sorted by the internationally agreed SOC order and by decreasing incidence of PTs within each SOC. This sorting order will be applied to all other tables, unless otherwise specified
- All treatment-emergent adverse events regardless of relationship and related by primary SOC, HLGT, HLT and PT, showing the number (%) of patients with at least 1 treatment-emergent adverse event, sorted by the internationally agreed SOC order. The other levels (HLGT, HLT, PT) will be presented in alphabetical order

All treatment-emergent adverse events by maximal severity, presented by primary SOC and PT, showing the number (%) of patients with at least 1 treatment-emergent adverse event by severity (ie, mild, moderate, or severe), sorted by the sorting order defined above

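### SAP 2.2 classifies patients who left the study by their reason for stopping IMP, and no output gives reasons for study withdrawal or the non-fatal AEs leading to it

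*SAP*

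**What the plan says.** SAP 2.2 lists the patient status categories for the clinical study report. Two concern leaving early. One is a plain count: "Patients who did not complete the study period as per protocol". The other carries a reason: "Patients who discontinued study period by main reason for permanent treatment discontinuation". The text that follows promises reason tables for treatment discontinuation only, for the overall group, the retreated group and the immediate (IAT) and delayed (DAT) alemtuzumab subgroups. For every category, "percentages will be calculated using the number of all enrolled patients as the denominator".

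In SAP 2.4.5.1 the overview row on discontinuation is "Treatment-emergent adverse event leading to permanent treatment discontinuation". The detailed tables and the by-patient listing that follow are also about stopping treatment. SAP section 3 carries the same item into the yearly interim report.

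The protocol keeps the two events apart. Section 10.3.1, on stopping IMP, says: "Permanent treatment discontinuation is any treatment discontinuation associated with the definitive decision from the Study Investigator or the patient not to re-expose the patient". Section 10.3 adds: "In any case, the patient should remain in the study as long as possible". Withdrawal from the study has its own section, 10.3.4. Section 8.1.1 says of alemtuzumab in this study: "There is no fixed treatment requirement or schedule".

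**The concern.** In a trial with scheduled dosing, stopping the drug and leaving the study often coincide, and one set of reasons can roughly serve for both. That does not carry over to TOPAZ. It is a follow-up study in which alemtuzumab is given only if the investigator decides on a further course. The SAP accordingly treats patients dosed in TOPAZ as a separate subset (2.3.1.1).

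The primary objective is long-term safety. Event rates per patient-year, the Kaplan-Meier relapse-free estimates and the EDSS mixed model without imputation all depend on why follow-up ended. If patients left because of non-fatal harm or worsening disease, a reader needs to see it to judge how far the remaining data represent the cohort. A table headed by reasons for stopping IMP answers a different question.

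**Working it through.** The documents give no figure on this point: no sample size calculation, no expected withdrawal rate and no number retreated. The check is a comparison of texts.

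**1. Two events in the protocol.**

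| | Permanent IMP discontinuation | Study withdrawal |
|---|---|---|
| Where defined | 10.3.1 to 10.3.3 | 10.3.4 |
| What it is | A decision against any further exposure | The patient ends participation |
| Follow-up afterwards | Continues, at least to study completion | Ends, with end-of-study assessments if possible |
| Reason required in the e-CRF | Yes (10.3.2) | Not stated |

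**2. What SAP 2.2 does with them.** It takes the patients from the right-hand column and classifies them by the reason from the left-hand column. No line gives reasons for study withdrawal as such.

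**3. The SAP applied literally to typical patients.**

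- *Never retreated in TOPAZ, leaves because of a non-fatal AE.* Counted as a non-completer with no reason. The reason-bearing line asks why IMP was stopped, which is either not applicable or records a decision about future courses. The AE appears in the general AE tables, and in the SAE or AESI listing if it qualifies, but nothing marks it as the cause of leaving.
- *Never retreated, lost to follow-up or withdraws by choice.* Treated the same way. Protocol 10.3.4 leaves the handling of patients lost to follow-up to the SAP. SAP 2.5.2 on missing data gives no such rule, and 2.5.3.1 only assigns early-withdrawal visits to analysis windows.
- *Retreated, stops IMP because of an AE, stays in the study.* Correctly captured by the AE tables for treatment discontinuation. This patient does not belong in a line about study leavers.
- *Retreated, stops IMP, later leaves for another reason.* Shown among study leavers under the reason for stopping IMP, which may differ in cause and date from the reason for leaving.
- *Dies on study.* Covered: SAP 2.4.5.1 counts AEs leading to death, and 2.4.5.2 tabulates deaths by study period and fatal AEs by system organ class and preferred term.

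**4. AE outputs.** The overview, tables and listing in 2.4.5.1 use treatment discontinuation. The listings show the action taken with study treatment, which matches what Protocol 10.4.2 asks investigators to record. No field or output links an AE to study withdrawal.

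**5. Denominators.** Disposition percentages use all enrolled patients. AE percentages use the safety population, which is everyone who signed consent (SAP 2.3.1). For stopping a TOPAZ course, the patients at risk are the retreated. If r is the retreated share, n/N is smaller than n/(rN) by a factor of 1/r. The documents do not give r, so the factor cannot be stated.

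**The case against.** The strongest reply is that the SAP 2.2 line is a wording slip. It sits under patient study status, counts people who left the study and breaks them down by a main reason. Reasons are promised for the overall group beside the retreated group, so some reason seems intended for patients never retreated. Protocol 11.2 promises a summary of patient discontinuation, Protocol 11.4 says all collected data will be reported, and SAP 1.5 declares no change to the protocol's statistics. A patient not retreated in TOPAZ can also have a recorded decision against further alemtuzumab, because the definition concerns re-exposure and the drug was given in the parent studies.

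Much of this stands, and it limits the point. A reader might infer that the report will say nothing about why patients left, or that deaths drop out of view. The documents do not support either: a discontinuation summary is promised, non-completers are counted, and deaths and fatal AEs have their own tables. A reader might also infer that the IMP-stopping reason will be blank for most leavers, or that percentages are diluted by a known factor. Neither can be shown without the retreated share. Reasons for stopping treatment are already to be shown for the retreated group, and the number retreated is itself a disposition row, so a reader could recompute the percentage.

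The slip explanation does not remove the problem. The sentence after the list repeats treatment discontinuation, the AE sections use it throughout, and the Protocol 11.2 commitment names no reasons. Followed as written, the SAP produces the wrong breakdown. A recorded decision against further courses is also not a reason for leaving the study.

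**Conclusion.** The point holds in a limited form. SAP 2.2 conflates study discontinuation with IMP discontinuation, and no planned output gives the reasons for study withdrawal or the non-fatal AEs leading to it. Fatal outcomes are covered.

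This is more than a missing detail, because a stated rule, followed literally, classifies study leavers by the wrong event in a study whose primary objective is long-term safety. It does not invalidate any planned safety or efficacy estimate. It withholds information needed to interpret them. No numerical size can be given. The practical weight depends on two unstated quantities: how many patients leave early, and how many of those had no alemtuzumab in TOPAZ. The conclusion assumes that the SAP will be programmed as written.

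**What to change.** In SAP 2.2, replace the line with: patients who discontinued the study by main reason for study discontinuation (AE, death, lost to follow-up, patient decision, other), for all enrolled patients and by IAT and DAT.

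Report reasons for IMP discontinuation, and AEs leading to it, separately with the retreated population as denominator.

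In SAP 2.4.5.1, add a table or listing of AEs leading to study withdrawal. First confirm that the e-CRF holds the main reason for withdrawal and a link from the AE to it. Protocol 10.3.2 requires the reason for stopping treatment to be recorded, but 10.3.4 and 10.4.2 do not show that these two items are collected. If the AE link is absent, a listing of patients withdrawn for an AE, with their ongoing events, could be considered.

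The same edit could state the handling of patients lost to follow-up that Protocol 10.3.4 leaves to the SAP.

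The cost is SAP wording and one or two extra outputs, provided the e-CRF fields exist. Patient care does not change.
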